7.2.4. Liver-Related Laboratory Evaluations

Liver-related abnormalities after initial study drug dosing will be examined and summarized using the number and percentage of subjects who were reported to have the following laboratory test values for postbaseline measurements:

- Aspartate aminotransferase (AST): (a) $> 3 \times \text{ULN}$, (b) $> 5 \times \text{ULN}$, (c) $> 10 \times \text{ULN}$, (d) $> 20 \times \text{ULN}$
- Alanine aminotransferase (ALT): (a) $> 3 \times \text{ULN}$, (b) $> 5 \times \text{ULN}$, (c) $> 10 \times \text{ULN}$, (d) $> 20 \times \text{ULN}$
- AST or ALT: (a) $> 3 \times \text{ULN}$, (b) $> 5 \times \text{ULN}$, (c) $> 10 \times \text{ULN}$, (d) $> 20 \times \text{ULN}$
- Total bilirubin: (a) $> 1 \times \text{ULN}$, (b) $> 2 \times \text{ULN}$
- Alkaline phosphatase (ALP) $> 1.5 \times \text{ULN}$
- AST or ALT $> 3 \times \text{ULN}$ and total bilirubin: (a) $> 1.5 \times \text{ULN}$, (b) $> 2 \times \text{ULN}$
- AST or ALT $> 3 \times \text{ULN}$ and total bilirubin $> 2 \times \text{ULN}$ and ALP $< 2 \times \text{ULN}$

The summary will include data from all postbaseline visits up to 30 days after the last dose date of B/F/TAF. For individual laboratory tests, subjects will be counted once based on the most severe postbaseline value. For both the composite endpoint of AST or ALT and total bilirubin, and the composite endpoint of AST or ALT, total bilirubin, and ALP, subjects will be counted once when the criteria are met at the same postbaseline visit date. The denominator is the number of subjects in the Safety analysis set with nonmissing postbaseline value of the tests in evaluation at the same postbaseline visit date.

Subjects with AST or ALT $> 3 \times \text{ULN}$ will also be listed.

In addition, baseline, postbaseline, and change from baseline in AST, ALT, ALP, and total bilirubin will be summarized by visit using descriptive statistics.

In addition, ALT elevation (ie, ALT $> 2 \times \text{Baseline}$ and ALT $> 10 \times \text{ULN}$) and ALT flare, defined as ALT elevations confirmed at two consecutive visits, will be evaluated and listed for subjects with HIV/HBV coinfection at baseline. The first occurrence of two or more consecutive ALT elevations will be identified as the ALT flare.

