9) Male subjects who are fertile and engage in heterosexual intercourse with women who are of child-bearing potential must agree to use protocol specified method(s) of contraception as described in [Appendix 5](#).

10) Male subjects must agree to refrain from sperm donation from first study drug dose until after the end of relevant systemic exposure

11) Life expectancy >1 year

12) Hepatic transaminases (AST and ALT)  $\leq$  5  $\times$  upper limit of normal (ULN)

13) Total bilirubin  $\leq$  1.5X ULN or normal direct bilirubin

14) Adequate hematologic function (absolute neutrophil count  $\geq$  750/mm^3 ( $\geq$  0.75 GI/L); platelets  $\geq$  50,000/mm^3 ( $\geq$  50 GI/L); hemoglobin  $\geq$  8.5 g/dL ( $\geq$  85 g/L))

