#### 7.4.6. Hepatitis C Management

If a subject tests positive for HCV RNA at screening or develops signs or symptoms of active Hepatitis C virus Gilead recommends that local medical practice is followed at the discretion of the Investigator. Study drug may be continued without dose interruption. Should the Investigator decide to initiate Hepatitis C treatment, the Investigator must contact the Gilead Medical Monitor to confirm that no drug-drug interactions with Hepatitis C medications are expected. Subjects should return to the clinic for scheduled or unscheduled follow up visit(s) according to local medical practice for laboratory evaluations. If Hepatitis C treatment is initiated, Investigators should use the Gilead provided retest laboratory kits to manage the active Hepatitis C.

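### SAP 7.2.4 counts liver-test thresholds with no baseline reference, so a subject unchanged from an eligible entry value can be counted in 9 of its 18 rows

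*SAP*

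**What the plan says.** SAP 7.2.4 opens: "Liver-related abnormalities after initial study drug dosing will be examined and summarized using the number and percentage of subjects" reported to have certain values at postbaseline measurements. The rows are:

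- AST, ALT, and AST or ALT, each at >3, >5, >10 and >20 x ULN
- total bilirubin >1 and >2 x ULN
- ALP >1.5 x ULN
- AST or ALT >3 x ULN with total bilirubin >1.5, and with total bilirubin >2 x ULN
- AST or ALT >3 x ULN with total bilirubin >2 x ULN and ALP <2 x ULN

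For single tests, "subjects will be counted once based on the most severe postbaseline value". For composites, "subjects will be counted once when the criteria are met at the same postbaseline visit date". Neither rule looks at baseline. The one baseline-relative rule in the section (ALT above twice baseline and above 10 x ULN) feeds a listing restricted to subjects with HIV/HBV coinfection.

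On entry, Protocol 4.2 criterion 12 allows AST and ALT up to 5 x ULN. Criterion 13 requires total bilirubin at or below "1.5X ULN or normal direct bilirubin", and its second branch carries no number. ALP is not mentioned. Protocol 4.3 excludes decompensated cirrhosis and recent acute hepatitis, but sets no numeric liver limit. Chronic hepatitis C is not excluded: Protocol 7.4.6 covers what follows "If a subject tests positive for HCV RNA at screening".

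**The concern.** The lower thresholds in the table lie inside the range that the protocol admits. A subject can cross them on the day of entry, keep the same values for 96 weeks, and still be counted among abnormalities found after dosing.

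This matters more here than in a controlled trial. There is one arm and no concurrent background rate, so a subject's own baseline is the only reference for judging a count. Safety and tolerability of the switch is a secondary objective, and Protocol 7.4.5 names potential hepatobiliary toxicity as something to watch for. A composite row showing one or two subjects will draw attention, and the table as specified cannot tell a reader whether those subjects changed.

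**Working it through.** The plan gives no figure on this point (SAP 1.3 bases the sample size on feasibility), so there is none to reproduce. The check applies the entry rule and the table rule to the same unchanged subject.

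**Rows in SAP 7.2.4.** AST 4 + ALT 4 + either 4 + bilirubin 2 + ALP 1 + two-part composite 2 + three-part composite 1 = 18.

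**Rows that an unchanged eligible value can meet.**
- AST >3, ALT >3, either >3: yes, because entry allows up to 5 (3 rows).
- The >5, >10 and >20 tiers: no, because 5 is not above 5.
- Bilirubin >1: yes, on either branch of criterion 13 (1 row).
- Bilirubin >2: yes, but only with normal direct bilirubin (1 row).
- ALP >1.5: yes, because there is no entry limit (1 row).
- The three composites: yes, but only with normal direct bilirubin, because each needs total bilirubin above 1.5 (3 rows).

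Total: 3 + 1 + 1 + 1 + 3 = 9.

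**Hypothetical subjects, same values at entry and at every visit (multiples of ULN).**

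| AST and ALT | Total bilirubin | Direct bilirubin | ALP | Eligible | Rows met | Composites met |
|---|---|---|---|---|---|---|
| 4 | 1.0 | normal | 1 | yes | 3 | 0 |
| 1 | 2.2 | normal | 1 | yes | 2 | 0 |
| 4 | 1.5 | abnormal | 1 | yes | 4 | 0 |
| 4 | 2.2 | normal | 1 | yes | 8 | 3 |
| 4 | 2.2 | normal | 1.8 | yes | 9 | 3 |

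**Same subject in the graded table.** On the scale in Protocol Appendix 4, ALT 4 x ULN is Grade 2 (>2.5 to 5) and bilirubin 2.2 x ULN is Grade 2 (>1.5 to 2.5). SAP 7.2.2.1 needs a rise of at least one grade, so the fourth subject has no treatment-emergent abnormality for these tests, yet is in all three composite rows of 7.2.4.

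**Weight of one subject.** 1/86 = 1.16 percentage points with the Safety Analysis Set of 86 shown in the SAP Appendix 7 mock table; 1/80 = 1.25 with the planned number. Both assume that all subjects are evaluable.

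**Chance of at least one.** The documents give no prevalence. If a proportion p of entrants exceeds a given threshold at baseline, P(at least one of 86) = 1 - (1 - p)^86:

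| Assumed p | 0.5% | 1% | 2% | 5% |
|---|---|---|---|---|
| P(at least one) | 0.35 | 0.58 | 0.82 | 0.99 |

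These values of p are assumptions for a single threshold. They say nothing about how often the joint condition for a composite occurs.

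**Would counting only newly met criteria be safe?** Take a subject at ALT 4 and bilirubin 2.1 with normal direct bilirubin at baseline, who rises to ALT 12 and bilirubin 6 with ALP below 2 throughout. All three composites were met at baseline (4 > 3; 2.1 > 1.5 and > 2; ALP < 2), so a newly met count records 0 in each, although both tests went from Grade 2 to Grade 4. The existing postbaseline count keeps this subject.

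**The case against.** The strongest reply is that this is a supplementary absolute-threshold screen and that baseline is handled elsewhere. Protocol 8.6.3 asks for treatment-emergent graded abnormalities and change from baseline, and SAP 7.2.1 and 7.2.2 provide both. SAP 7.1.7.3 summarises treatment-emergent hepatic events, including serious ones, from 15 SMQs. SAP 7.2.4 lists every subject with AST or ALT >3 x ULN, which covers every composite case, and SAP 7.2 lists all serum chemistry by subject in time order. With 86 subjects, individual review is practical. The secondary safety endpoints are adverse events, and no decision rule uses this table.

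Most of that stands and limits the weight of the point. It does not remove it. The graded tables work one test at a time, so they give no composite against baseline. The change summaries are aggregate. The 7.2.4 listing is not specified to show baseline values, and it omits subjects who meet only a bilirubin or ALP row. Working back through the full chemistry listing leaves the printed counts as they are.

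A reader might infer that the table attributes pre-existing abnormalities to B/F/TAF. The text does not support that: the opening sentence states when values were measured, and the SAP reserves the treatment-emergent label for its other rule. A reader might also infer that the counts will in fact be inflated, or that coinfected subjects are known to be numerous. SAP 5.2 only defines HIV/HBV coinfection as a category to summarise, Protocol 7.4.6 only provides for HCV-positive subjects, and neither gives a frequency.

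**Conclusion.** The point holds as a limit on how one safety table can be read. Nine of 18 rows can be met with no change from an eligible value, and the three composites among them depend on the normal-direct-bilirubin branch of criterion 13. Nine of 18 describes what is possible, not what is likely; the frequency is unknown. Each such subject would add about 1.2 percentage points to every row met, if all 86 are evaluable.

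The row count assumes that baseline satisfies the entry limits. Eligibility is judged at screening, whereas SAP 3.8.1 takes the last value on or before Study Day 1, so a baseline value could lie outside them.

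The primary endpoint and the adverse-event endpoints are unaffected. Nothing here shows that the trial's liver safety conclusions would be wrong. This is a worthwhile, inexpensive improvement to the SAP.

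**What to change.** In SAP 7.2.4, for every row:

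1. Keep the postbaseline absolute-threshold count as it is.
2. Add the number meeting the same criterion at baseline. For composites, use tests from the same baseline date.
3. Split the postbaseline count into met at baseline, not met at baseline, and baseline missing.

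Do not replace the existing count with the newly met count, for the reason shown in the worsening example.

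In the listing of subjects with AST or ALT >3 x ULN, show baseline AST, ALT, ALP, total bilirubin and direct bilirubin beside the postbaseline values, so that worsening from an already raised baseline is visible.

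The SAP has precedents: urine protein categories are tabulated by baseline category (7.2.5.2), and ECG results appear as a shift table (7.5). No new data are needed, since Protocol 6.9 collects all five tests at every visit. The cost is extra columns and small cell counts. Because the SAP is already signed, the change can be made as a revision or documented in the clinical study report, as SAP Section 1 provides.

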7.2.5. Renal-Related Laboratory Evaluations

7.2.5.1. Serum Creatinine and eGFR_{CG}

Baseline, postbaseline, and change from baseline in serum creatinine and eGFR_{CG} will be summarized by visit using descriptive statistics.

Median (Q1, Q3) of change from baseline in serum creatinine and eGFR_{CG} over time will be plotted.

7.2.5.2. Urine Creatinine, Urine Retinol Binding Protein to Creatinine Ratio, Beta-2-Microglobulin to Creatinine Ratio, and Urine Protein to Creatinine Ratio

Baseline, postbaseline, and change from baseline in urine creatinine will be summarized by visit using descriptive statistics. Change from baseline will be tested using the Wilcoxon signed rank test.

Baseline, postbaseline, change from baseline, and percentage change from baseline in urine RBP to creatinine ratio and beta-2 microglobulin to creatinine ratio will be summarized by visit using descriptive statistics. Change from baseline and percentage change from baseline will be tested using the Wilcoxon signed rank test.

Subjects will be classified into 4 categories based on their UP and UPCR results: The categories will be (1) UP $< 4.0 \text{ mg/dL}$, (2) UPCR $< 200 \text{ mg/g}$, (3) UPCR $> 200 \text{ mg/g}$, and (4) missing, where UPCR will only be calculated when UP $\geq 4.0 \text{ mg/dL}$. The number and percentage of subjects in each UP and UPCR category will be summarized by baseline category at Weeks 4, 12, 24, 48, 60, 72, 84 and 96.

Median (Q1, Q3) percentage change from baseline in urine RBP to creatinine ratio and beta-2 microglobulin to creatinine ratio over time will be plotted.

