Blood and urine for selected evaluations of renal safety, inflammation, and platelet and coagulation function will be collected at Day 1, Weeks 4, 12, 24, 48, 60, 72, 84, and 96. A portion of the biomarker blood sample obtained at Day 1, Weeks 4, 12, 24, 48, 60, 72, 84, and 96 may be utilized to assess study drug pharmacokinetics (PK). This will be a random sample with the date and time of the subject's last medication dose recorded.

Site and/or Stratum Enrollment Limits

Approximately 30 study sites in Europe participated. Approximately 80 subjects who meet the eligibility criteria will be enrolled in the study.

Study Duration

The treatment duration specified in the protocol was 96 weeks CCI [REDACTED] However, all subjects will discontinue the study at Week 96; therefore treatment duration will be up to 96 weeks, followed by a 30 day follow-up.

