1.3. Sample Size and Power

The sample size is based on feasibility of conducting a study with ≥ 65 year old subjects.

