3.5. Multiple Comparisons

Adjustments for multiplicity will not be made, because no formal statistical testing will be performed in this study.

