3.7. Data Handling Conventions and Transformations

Laboratory data that are continuous in nature but are less than the lower limit of quantitation or above the upper limit of quantitation will be imputed as follows except for urine creatinine:

- A value that is 1 unit less than the limit of quantitation will be used for calculation of descriptive statistics if the datum is reported in the form of “ $< x$ ” (where x is considered the limit of quantitation). For example, if the values are reported as < 50 and < 5.0 , values of 49 and 4.9, respectively, will be used for calculation of summary statistics. An exception to this rule is any value reported as < 1 or < 0.1 , etc. For values reported as < 1 or < 0.1 , a value of 0.9 or 0.09, respectively, will be used for calculation of summary statistics.
- A value that is 1 unit above the limit of quantitation will be used for calculation of descriptive statistics if the datum is reported in the form of “ $> x$ ” (where x is considered the limit of quantitation). Values with decimal points will follow the same logic as above.
- The limit of quantitation will be used for calculation of descriptive statistics if the datum is reported in the form of “ $\leq x$ ” or “ $\geq x$ ” (where x is considered the limit of quantitation).

For urine creatinine, a value of “ < 1 ” is handled as a missing value in its summary and the calculation of related ratios. Urine protein to creatinine ratio (UPCR) is not calculated if the urine protein value (UP) used for the ratio calculation from the same accession number is under the lower limit of quantification (ie, < 4.0 mg/dL).

Logarithm (base 10) transformation will be applied to HIV-1 RNA data for efficacy analysis. HIV-1 RNA results of ‘No HIV-1 RNA detected’ and “ <20 cp/mL HIV-1 RNA Detected” will be imputed as 19 copies/mL for analysis purposes.

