7.2.1. Summaries of Numeric Laboratory Results

Descriptive statistics will be provided for each laboratory test specified in the study protocol as follows:

- Baseline values
- Values at each postbaseline analysis window
- Change from baseline at each postbaseline analysis window
- Percentage change from baseline to each postbaseline analysis window (if specified)

A baseline laboratory value will be defined as the last nonmissing value obtained on or prior to the date of first dose of B/F/TAF. Change from baseline to a postbaseline visit will be defined as the postbaseline value minus the baseline value. The mean, median, Q1, Q3, minimum, and maximum values will be displayed to the reported number of digits; SD values will be displayed to the reported number of digits plus 1.

In the case of multiple values in an analysis window, data will be selected for analysis as described in Section [3.8.3](#).

Calcium Corrected for Albumin

Calcium corrected for albumin will be calculated and summarized for the study. The following formula will be used when both serum calcium and albumin results for a given blood drawn are available and serum albumin value is < 4.0 g/dL.

- Calcium corrected for albumin (mg/dL) = serum calcium (mg/dL) + 0.8 x (4.0 - albumin (g/dL)).

Toxicity grading for calcium will be applied based on the corrected values.

Estimated GFR

The Cockcroft-Gault (CG) formula will be used to calculate eGFR_{CG}:

- eGFR(CG) (mL/min) = $\frac{[(140 - \text{age (yrs)}) \times \text{weight (kg)} \times (0.85 \text{ if female})]}{(\text{SCr (mg/dL)} \times 72)}$, where weight is total body mass in kilograms.

Additionally, for baseline values only, the CKD-EPI (cystatin C) formula will be used to calculate eGFR_{CKD EPI, cysC}:

- eGFR_{CKD EPI, cysC} (mL/min/1.73 m²) = $133 \times \min(\text{Scys}/0.8, 1)^{0.499} \times \max(\text{Scys}/0.8, 1)^{1.328} \times 0.996^{\text{Age}} [\times 0.932 \text{ if female}]$, where Scys is serum cystatin C (mg/L), min (Scys/0.8,1) indicates the minimum of Scys/0.8 or 1, and max (Scys/0.8,1) indicates the maximum of Scys/0.8 or 1.

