Appendix 7. Programming Specification

1. Subject disposition mockup table

	B/F/TAF
Subjects Screened	xx
Screen Failure Subjects Who Were Not Enrolled	x
Subjects Met All Eligibility Criteria and Not Enrolled	x
Subjects Enrolled	86
Subjects Enrolled and Never Treated	0
Subjects in Safety Analysis Set	86
Subjects in Full Analysis Set	xx
Subjects Completed Study Drug	0
Subjects Prematurely Discontinuing Study Drug	xx (x.x%)
Reason for Prematurely Discontinuing Study Drug	
Reason 1	xx (x.x%)
Reason 2	xx (x.x%)
Reason x	xx (x.x%)
Subjects Completed Study	0
Subjects Prematurely Discontinuing Study	xx (x.x%)
Reason for Prematurely Discontinuing Study	
Reason 1	xx (x.x%)
Reason 2	xx (x.x%)
Reason x	xx (x.x%)

2. Defining ARV Regimen at Study Entry

All subjects are expected to enter the study on E/C/F/TAF FDC or FTC/TDF + 3rd agent.

Using the ARV raw dataset, include all prior and/or current ARVs (ARV.INGRED where ARV.CMSCAT = 'Prior ARV' or 'Current ARV'), taken on or up to 2 day prior to first dose date.

When determining the ARV regimen at study entry, please use the following rules:

- The ARV regimen at study entry will be recorded as 3rd Agent + FTC/TDF (note the reversed order, as this is due to clinical trials evaluating novel 3rd agents). When ordering the 3rd Agent medications, use the following order to assign priority:

INGRED	Priority	INGRED	Priority
EFV FTC TDF	1.2	RAL	3.2
EVG COBI FTC TDF	1.3	EFV	4.1
FTC RPV TDF	1.4	ETR	4.2
ATV COBI	2.1	NVP	4.3
DRV COBI	2.2	RPV	4.4
LPV RTV	2.3	ABC 3TC	5.1
ATV	2.4	FTC TDF	5.2
DRV	2.5	ABC	5.3
COBI	2.6	FTC	5.4
RTV	2.7	3TC	5.5
		TDF	5.6

- For all ingredients, replace “_” with “/”
- Make the following replacements to the ingredients:

Replace “DTG/ABC/3TC” with “ABC/DTG/3TC”

Replace “ATV/COBI” with “ATV/co”

Replace “DRV/COBI” with “DRV/co”

Replace “LPV/RTV” with “LPV/r”

- Once the ingredients have been updated and assigned an appropriate priority, transpose the ingredients (by subject) and concatenate each column with a “+” following the priority specified above

To illustrate these rules, suppose a subject is on ATV, RTV, and FTC_TDF. This would translate into “ATV+RTV+FTC/TDF”. If, instead, the subject was on LPV_RTV and FTC_TDF, their regimen would be presented as “LPV/r+FTC/TDF”.

Note: The following data issues should be queried:

- If the subject does not have either EVG/COBI/FTC/TDF or FTC/TDF in their ARV regimen at study entry

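### The signed rank test on percentage change in the urine RBP and beta-2-microglobulin ratios leans toward an increase even when nothing has changed

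*SAP*

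**What the plan says.** SAP 7.2.5.2 summarises the urine RBP to creatinine and beta-2-microglobulin to creatinine ratios by visit and adds: "Change from baseline and percentage change from baseline will be tested using the Wilcoxon signed rank test". Change is the simple difference: SAP 7.2.1 states that "Change from baseline to a postbaseline visit will be defined as the postbaseline value minus the baseline value". No formula is given for percentage change, so the usual 100 × (post − baseline)/baseline is assumed here.

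Neither document log-transforms these ratios. The one log transformation, in SAP 3.7, is for viral load: "Logarithm (base 10) transformation will be applied to HIV-1 RNA data for efficacy analysis". SAP 7.2.5.2 also plans a figure: "Median (Q1, Q3) percentage change from baseline in urine RBP to creatinine ratio and beta-2 microglobulin to creatinine ratio over time will be plotted".

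On the standing of the tests, SAP 3.5 says: "Adjustments for multiplicity will not be made, because no formal statistical testing will be performed in this study". This does not fit with the tests that 7.2.5.2 plans. No significance level is stated for them.

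**The concern.** The signed rank test adds up the ranks of the positive differences and compares the sum with what symmetry about zero would give. For a positive, ratio-type quantity, percentage change has a floor at −100% and no ceiling, so it is skewed to the right even when the treatment does nothing. The p-value then partly measures the skewness of the scale.

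These ratios are renal safety evaluations. Protocol 1.1 names nephrotoxicity as an identified risk of TDF, and some subjects switch from TDF-containing regimens. A test that leans upward can report a worsening that is not there, or miss a real fall. SAP Table 3-3 has eight post-baseline windows, so two markers give 2 × 8 = 16 such p-values, all unadjusted. Each also sits beside a test of absolute change on the same data, with no statement of which one to read when they disagree.

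**Working it through.** The plan states no figure for this test, so there is nothing to reproduce first.

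**Inputs from the documents.** About 80 subjects planned (SAP 1.2); 86 in the Safety Analysis Set (mock disposition table, SAP Appendix 7). The sample size rests on feasibility (SAP 1.3), so it supplies no SD, level or effect size.

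**Assumptions.** Two-sided 5%; log-normal values; SD of log(post/baseline) from 0.1 to 1.0; between-subject log SD 0.8 (affects only the absolute-change test); n=60 added to allow for missing or non-calculable ratios.

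**Step 1: direction.** Let R = post/baseline. If nothing has changed and the two values are exchangeable, R and 1/R have the same distribution. For r > 1:

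- a rise to R = r gives a change of r − 1;
- the mirror-image fall to R = 1/r gives −(1 − 1/r);
- since r − 1 = r × (1 − 1/r), the rise is r times as large in absolute size.

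Each rise therefore outranks its mirror-image fall. Take four subjects with ratios 2, 1/2, 1.25 and 0.8. The percentage changes are +100, −50, +25 and −20, with ranks 4, 3, 2 and 1. The positive rank sum is 4 + 2 = 6 and the negative is 3 + 1 = 4. On the log scale each pair ties, and both sums are 5. None of this needs log-normality.

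**Step 2: size under no change.** 20,000 simulated trials per cell, signed rank test with normal approximation. Rejection rate of the percentage-change test:

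| SD of log(post/baseline) | n=60 | n=80 | n=86 |
|---|---|---|---|
| 0.1 | 5.0% | 5.4% | 5.3% |
| 0.2 | 6.5% | 6.8% | 6.8% |
| 0.3 | 8.1% | 9.2% | 9.7% |
| 0.5 | 13.0% | 16.2% | 16.8% |
| 0.7 | 18.9% | 23.9% | 25.8% |
| 1.0 | 28.7% | 37.3% | 39.1% |

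Increases make up 70-73% of these rejections at SD 0.1, 83-88% at 0.2, and 91% or more from 0.3. In the same cells the absolute-change test rejects in 4.7-5.2% of trials and the log-ratio test in 4.4-5.1%. With heavier tails (t with 4 df, n=80) the percentage-change rates are 5%, 6%, 7%, 11%, 16% and 26%.

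A second simulation put the SD on each measurement, so that SD of the log ratio = 1.414 × per-measurement SD. At n=86, a per-measurement SD of 0.5 (log-ratio SD 0.71, CV about 53%) gives 26.5%, close to the 25.8% tabulated at 0.7. A per-measurement SD of 0.7 (log-ratio SD 0.99) gives 38.5%, close to the 39.1% at 1.0. In the first of these cases the pseudo-median that the test targets is about +11.6%, although the true median change is zero.

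**Step 3: disagreement between the two planned tests.** Under no change at n=80, percentage change is significant while absolute change is not in 2%, 4%, 6%, 13%, 21% and 35% of trials, in the order of SDs above.

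**Step 4: a true 20% fall, n=80** (10,000 trials per cell). Share of trials detecting it:

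| SD of log(post/baseline) | Percentage | Absolute | Log ratio |
|---|---|---|---|
| 0.3 | 100% | 100% | 100% |
| 0.5 | 79% | 94% | 97% |
| 0.7 | 29% | 71% | 78% |
| 1.0 | 5% | 42% | 49% |

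**The case against.** The strongest reply is that little hangs on these p-values. SAP 3.5 disclaims formal testing, Protocol 8.6.3 plans only summaries of observed laboratory data, and no decision rule or primary or secondary efficacy endpoint uses them. The same SAP sentence supplies a test of absolute change with the right size. The plotted median percentage change averages within 1.3 points of zero under no change. Both tests are significant upward together in only 2.0-2.7% of null trials, so a careful reader would see a conflicting pair and discount it. An over-called increase in a renal marker is also an error toward caution. Formally, the test remains valid for symmetry of percentage change about zero; exchangeability is a null the SAP never states. Finally, the size is unknown, and at an SD of 0.1 it is negligible.

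Most of this stands, and it limits the harm. It does not rescue the test. Symmetry of percentage change is not what a reader means by no change from baseline. The disclaimer in 3.5 explains the lack of a multiplicity adjustment but does not correct a p-value biased on its own scale. Relying on readers to discount one of two conflicting tests works only if the SAP says which one to discount. The caution argument also covers one direction only: at SDs of 0.5 and above, the test loses real falls.

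**Conclusion.** The concern holds. The signed rank test on percentage change in these two ratios is biased toward an increase. That direction follows from exchangeability alone. The size is a range over assumptions, not an estimate for this trial: at n=80 to 86, from about 5% at a log-ratio SD of 0.1 to 37-39% at 1.0, given log-normal values and a two-sided 5% level. Heavier tails reduce it; at SD 0.5 and n=80 the rate is 11% instead of 16%.

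The consequence is a misleading safety p-value that can contradict its companion test. It is not a wrong primary conclusion. The change should be made, but the trial's main results do not depend on it.

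**What to change.** In SAP 7.2.5.2, replace the signed rank test on percentage change with a test of log(post-baseline/baseline), either signed rank or one-sample t, and report the geometric mean ratio with its 95% CI. The t test is the natural partner to that interval, because a signed rank p-value and a geometric mean ratio target the same quantity only when the log ratios are symmetric. Keep the median (Q1, Q3) percentage change summary and the planned plot, without a p-value. Add a clause saying whether the log-ratio or the absolute-change result is the one to read.

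If the sponsor prefers no further testing, in line with SAP 3.5, simply deleting the percentage-change p-value also removes the bias.

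The cost is one sentence in the SAP and a log transform in the code. No new data are needed. The logs can always be computed, because SAP 3.7 imputes values below quantitation as positive numbers and treats unquantifiable urine creatinine as missing. SAP Section 1 provides for changes after finalisation to be documented in the clinical study report.
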